This is quasi-randomized wait-list controlled trial. Once enrolled, participants will undergo T1 assessments consisting of the primary outcome measures for each aim (described above and attached) and other relevant factors (e.g. demographics, clinical characteristics, motor function). Participants will be randomly assigned (coin flip) to one of two groups: ID or WC group. Although our aim is to randomize participants to the different groups, if someone has a strong preference or inability to participate in one group or the other due to scheduling issues, we will try to accommodate his/her preferences. Each group will have 7-10 participants, a typical size for ID classes. This ensures enough participants to create a cohesive group, but also to provide an appropriate level of safety. The ID group will participate in a 12-week intervention where the group will meet once a week for a 1-hour IMPROVment® class. Participants in the WC group will continue with their regular routine for 12 weeks. After 12 weeks, all participants will complete T2 testing. Then WC participants will participate in the same IMPROVment® method for the following 12 weeks followed by T3 testing.

E2 Subject Selection and Withdrawal

2.a Inclusion Criteria

Inclusion criteria for this study include over 50 years old, PD diagnosis with Hoehn and Yahr stage 1-3 (mild to moderate), independently walks at least 3 meters and ability to comprehend and follow simple verbal cues.

2.a Exclusion Criteria

Exclusion criteria of this study include, a Montreal Cognitive Assessment score less than or equal to 21 (indicating cognitive impairment that may interfere with class participation), diagnosis of other severe comorbidities, and contraindications to physical activity. In addition, participants must attend at least ten of the twelve classes for their data to be included in analysis (they will still be allowed to participate in the classes).

2.b Ethical Considerations

Participants will be given the choice to be involved in the study and may withdraw at any time without penalty.

2.c Subject Recruitment Plans and Consent Process

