Classes will take place at the APDA in their group fitness room. Participants will use chairs and music during the class. Class will be instructed by an occupational therapy (OT) student that has trained as a dancer for 20 years and is certified to administer the IMPROVment® method after attending an in-person training by its original creators and continues to receive feedback to better the administration of IMPROVment®⁷. Class will begin and end with participants sitting in a circle formation to eliminate any feelings of hierarchy among the participants by creating a unified group. The classes consist of three parts: seated exercise, standing barre work, and across the floor movement (refer to Table 1). Movement cues are given by the instructor to the participants and progress through the themes of isolation, shape, time, flow, space/direction, and effort (refer to Table 2). Classes will be structured by using a set class protocol created by the IMPROVment team to ensure consistency in the method delivery. Music that is popular with the age demographic will be played throughout the entire class. Trained OT students in the Cognitive and Occupational Performance Lab (PI: [name]) and the APDA's certified physical therapist ([name], DPT) will attend all classes to ensure participant safety.

Please see Appendix 2 for a detailed list of exercises that comprise class structure.

F4 Safety and Adverse Events

4.a Safety and Compliance Monitoring

Trained occupational therapy graduate students in the Cognitive and Occupational Performance Laboratory (PI: [name]) and the APDA's certified physical therapist ([name], DPT) will attend all classes to ensure participant safety. We do not anticipate any serious adverse events; however, class participation may increase the risk for falls and minor resulting injuries (e.g., bruises, scrapes). We expect this occurrence to be low if at all present, as the participants have relatively low fall risk and precautionary measures are in place to prevent falls (i.e. certified PT and OT students present at all times to monitoring participants' safety, safety modifications [e.g. sitting in a chair]).

4.b Medical Monitoring

NA

4.c Definitions of Adverse Events

NA

4.d Classification of Events

NA

4.e Data Collection Procedures for Adverse Events

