See Adverse Event Reporting Form in Appendix 3. Data on the number and type of adverse events will be collected and reported when study results are disseminated.

4.f Reporting Procedures

See Adverse Event Reporting Form in Appendix 3.

4.g Adverse Event Reporting Period

Adverse events will be reported to the PI immediately (within one day), and the participant will be encouraged to report them to his/her primary care physician or neurologist within the week.

4.h Post-study Adverse Event

NA

G Statistical Plan

G1 Sample Size Determination and Power

Each group will have 7-10 participants, a typical size for ID classes. This ensures enough participants to create a cohesive group, but also to provide an appropriate level of safety. Since this is a pilot study, power analyses were not conducted. Rather, data from this study can be used to power future studies. Although attrition is not anticipated, we aim to recruit 10 participants per group to ensure there are at least 7 participants in the class.

G2 Interim Monitoring and Early Stopping

NA

G3 Analysis Plan

Aim 1: Investigate the effects of IMPROVment® on cognition for people with PD.
Cognition will be assessed at pre (T1) and post (T2) using the NIH (CB), AUT, and WCPA. Scores obtained in these assessments will be compared across time point and group using mixed model ANOVA.

Aim 2: Investigate the effects of IMPROVment® on daily functions for people with PD.
Daily function will be measured at pre (T1) and posttest (T2) using the OARS-EX and SPDSA. Scores will be compared across time point and group using mixed model ANOVA.

G4 Statistical Methods

See above. Analysis will be conducted with IBM SPSS software.

G5 Missing Outcome Data

Participants with missing data will be excluded from analyses involving those data. Since this is a small pilot study, we intend to maximise the use of data we can collect.

G6 Unblinding Procedures

NA (this is not a blinded study)

H Data Handling and Record Keeping

H1 Confidentiality and Security

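### No falls or adverse-event enquiry is scheduled in either group, so the promised adverse-event totals cannot be interpreted by group

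*Combined protocol and SAP*

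**What the plan says.** Section 4.a of the combined protocol and SAP states that "class participation may increase the risk for falls and minor resulting injuries". Falls are the only physical risk listed in section 2.e. The monitoring described in 4.a is by occupational therapy students and a physical therapist, who "will attend all classes to ensure participant safety".

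On data collection, section 4.e says "See Adverse Event Reporting Form in Appendix 3" and then commits to an output: "Data on the number and type of adverse events will be collected and reported when study results are disseminated". Section 4.f points to the same form. Section 4.g sets a one-day limit for telling the principal investigator, but no window over which events are collected. Adverse-event definitions (4.c), classification (4.d) and post-study events (4.h) are marked as not applicable.

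On contact with participants, section E1 says "The ID group will participate in a 12-week intervention where the group will meet once a week for a 1-hour IMPROVment® class", whereas "Participants in the WC group will continue with their regular routine for 12 weeks".

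Section F2 lists the assessments at T1, T2 and (for WC) T3, plus a mood questionnaire at each class. No falls or adverse-event question is among them.

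**The concern.** In a two-group study a reader will naturally set the event count in one group against the count in the other, above all when the protocol says the intervention may raise the risk of falling. That reading needs the same chance of detecting an event in both groups. Here one group meets staff every week and the other meets none between T1 and T2. Neither is asked about falls, so recording depends on what staff see and what participants happen to mention.

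At stake is the meaning of the safety summary. A fall at home by an ID participant might be mentioned at the next class, while the same fall in WC has no scheduled occasion on which to be mentioned. Because 4.c and 4.d are left blank, the plan does not say whether a home fall counts as an event at all. Section G1 intends the data to help power future studies, so a distorted safety comparison could be carried forward. The cognition and daily-function aims are not affected.

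**Working it through.** The plan states no fall rate, capture rate or safety analysis, so there is no figure to reproduce. The check is a comparison of sections, followed by arithmetic on assumed values.

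**1. Is there any enquiry about events?**

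- F2, T1/T2/T3: cognitive tests, the UPDRS motor examination, and questionnaires on daily function, social participation, anxiety, sleep, fatigue and depression. None is described as counting falls or injuries.
- OARS-Ex, as reproduced, asks about difficulty and help needed in daily activities, not falls.
- Appendix 4, used at each class, rates mood and well-being only.
- Appendix 3 is completed once an event is known. It does not say who asks, whom, or when.
- G3 contains no adverse-event analysis.

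**2. Scheduled staff contact between T1 and T2**

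- ID: 12 classes of 1 hour, so 12 hours out of 12 × 7 × 24 = 2,016 hours, or 12/2,016 = 0.6%.
- WC: none.

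So about 99.4% of ID time and all WC time passes without study staff present. Events in that time can be reported spontaneously, but nothing prompts the report.

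**3. What unequal capture would do (assumed values)**

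Apparent rate ratio = true rate ratio × (fraction captured in ID ÷ fraction captured in WC). With a true ratio of 1:

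| Captured in ID | WC 80% | WC 50% | WC 30% | WC 10% |
|---|---|---|---|---|
| 90% | 1.125 | 1.8 | 3.0 | 9.0 |
| 60% | 0.75 | 1.2 | 2.0 | 6.0 |

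Example: at an assumed 0.5 falls per person over 12 weeks and 10 per group, each group has 0.5 × 10 = 5 true falls. At 90% and 30% capture, 5 × 0.9 = 4.5 are recorded in ID and 5 × 0.3 = 1.5 in WC.

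**4. Where a difference would come from**

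Background falls that happen to occur in class hours: 0.5 × 10 × 12/2,016 = 0.03. Direct observation of background falls therefore adds almost nothing. A sizeable distortion would have to come from weekly contact prompting ID participants to mention falls elsewhere.

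**5. What equal enquiry would and would not give**

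Equal capture returns the spurious ratio to 1.0. It does not make the comparison a test. Two-sided Fisher exact power at alpha 0.05, for assumed proportions of participants who fall, with the size needed for 80% power by normal approximation:

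| Proportions compared | 7 per group | 10 per group | Per group for 80% |
|---|---|---|---|
| 10% vs 20% | 0.2% | 1.2% | 199 |
| 20% vs 40% | 2.8% | 5.8% | 82 |
| 30% vs 60% | 8.3% | 12.3% | 42 |
| 20% vs 60% | 15.4% | 25.3% | 23 |

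**The case against.** The strongest reply is that the plan never offers a between-group comparison of falls. It promises counts by number and type, fall risk is not an aim, and G3 has no safety analysis. That stands: the gap limits what the counts can mean and contradicts no stated analysis.

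It can also be said that the risk the plan has in mind is falling during class, where trained staff are always present. That stands too. In-class events are observed over known hours and describe in-class safety.

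Nor is staff presence declared to be the sole means of finding events. Appendix 3 separates the event date from the date staff learned of it, so unwitnessed events can be recorded, and the one-day reporting rule is not confined to ID or to class. The accurate statement is that outside events are not solicited, not that they would be missed.

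A reader might infer that ID would necessarily show more events because only ID is watched. The documents do not support this: direct observation covers 0.6% of the time, and the ratios above fall on both sides of 1. A reader might also cite the wide limit on risk after zero events in 7 to 10 people. That follows from group size alone and would be the same with perfect ascertainment, so it is not a consequence of this gap.

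Finally, equal enquiry will not deliver a test of fall risk. That is correct, and the fix should not be presented as doing so.

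**Conclusion.** The concern holds in a limited form. The plan names falls as a risk and promises event counts, yet schedules no enquiry in either group, and only ID has staffed contact between T1 and T2. The chance of recording an event therefore depends on group. In-class counts are usable for in-class safety; total counts cannot be interpreted by group.

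The size cannot be fixed from the documents. On the assumed capture fractions, a true ratio of 1 could appear as anything from 0.75 to 9.0, and the direction is not known. This rests on F2 being the full list of planned assessments and on no solicitation being arranged elsewhere. The consent pages are not available, so they may tell participants to report injuries.

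The change is worth making because it is cheap and removes an avoidable difference in detection. Even then the counts stay descriptive: groups of 7 to 10, and allocation that can follow participant preference (E1, 2.d), do not support a test of fall risk.

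**What to change.** In F2 and 4.e, add wording to this effect:

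- At T2, every participant in both groups is asked the same question about falls and injuries since the previous test; WC is asked again at T3. Participants who stop classes or testing are asked too, where they agree. Section 2.f allows people to keep dancing while leaving testing, and a question tied only to attended visits would miss them.
- Each positive answer is entered on the Appendix 3 form with the event date and marked in-class or outside class. Dates matter because J5 puts a gap between T2 in November and the start of WC classes in January.
- These events are reported by group and period with denominators, separately from events observed by staff in class. State whether participants attending fewer than ten classes, whose data E2 excludes from analysis, are included in the safety counts.
- Sections 4.c and 4.g state what counts as an event and over what period events are collected.
- G3 states that the counts are descriptive and are not a test of fall risk.

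The cost is a few minutes per participant at visits that already take place, plus a brief contact with those who stop. The drawback is recall over 12 weeks, and longer between T2 and T3. Recall may not be equally accurate in the two groups, since the study is unblinded and weekly contact could prompt memory in ID.

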Parkinson's disease is a neurodegenerative disease that results in various deficits, including cognitive impairments, for which there is a lack of interventions. Improvisational dance (ID) is spontaneously generated movement, similar to how one moves in everyday life. ID requires the integration of cognitive capacities to execute movements, and thus may strengthen cognitive processes involved in daily life function. ID has been shown to improve motor function in people with PD. The purpose of this study is to understand the effects of ID on cognition and daily function for people with PD. Specifically, it will test the effect of IMPROVment®, a method of ID designed for people with PD, on cognition and daily function. We will conduct a quasi-randomized wait-list controlled trial. Participants will be recruited and screened for eligibility through the St. Louis Chapter American Parkinson's Disease Association. Inclusion criteria includes: 50 years or older, PD diagnosis (mild to moderate), follows simple verbal cues, walks at least 3 meters independently, no contraindications in physical activity, mild cognitive impairment (determined by MOCA score), and no diagnosis of other severe comorbidities. The target sample size is 15-20 participants. Once enrolled, participants will undergo baseline testing (T1). Then participants will be randomly assigned to one of two groups: ID or waitlist control (WC). Participants in the ID group will begin a 12-week intervention where the group will meet once a week for a 1-hour IMPROVment® class. Participants in the WC group will continue with their regular routine for 12 weeks. After 12 weeks, all participants will complete Time 2 testing (T2; primary endpoint). Then WC participants will participate in the same IMPROVment® class for the following 12 weeks followed by Time 3 testing (T3; exploratory endpoint). For primary analysis, assessment scores will be compared across time point (T1, T2) and group (ID, WC) using mixed model ANOVA. Our results will provide further information on the effects of the IMPROVment® method for people with PD.

A2 Primary Hypothesis

The *central hypothesis* is that engagement in an improvisational dance (ID) class will benefit cognition and daily function among people with PD.

A3 Purpose of the Study Protocol

The purpose of this study protocol is to detail the various aspects of this study.

B Background

B1 Prior Literature and Studies

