Another benefit to ID classes is that there is no right or wrong, and no set movements. These features allow free expression through movement and broad accessibility to the population of people with PD in which there is a wide range of functional capacity. Participants involved in more structured dance classes have reported feeling overwhelmed by the strict nature of the class, so they may prefer the self-determination of ID¹⁴.

Community-based programs promote activity engagement among people with PD.

Aside from dance itself, ID classes provide a fun, social form of activity engagement for participants. Research shows that people with PD that engage in PD-specific community-based programs are more likely to participate in everyday activities and roles^{21, 22}. Not only does participation in community-based programs increase activity participation, research suggests that community engagement increases participation in activities that people with PD ceased at the onset of their diagnosis²².

C Study Objectives

C1 Primary Aim

Investigate the effects of IMPROVment® on cognition for people with PD.

To test this aim, participants’ cognition will be assessed using the NIH Toolbox Cognitive Battery (NIH (CB)), the Alternate Uses Task (AUT), and the Weekly Calendar Planning

Activity (WCPA). Cognitive test scores will be compared across time points (T1, T2) and between groups (ID, WC) using a mixed model repeated measures ANOVA. We hypothesize that IMPROVment® will have positive effects on the cognitive abilities of people with PD.

C2 Secondary Aim

Investigate the effects of IMPROVment® on daily functions for people with PD.

Participants will also complete two questionnaires to assess daily function: Older Americans Resources and Services Scale- Extended Version (OARS-Ex) and PROMIS Satisfaction with Participation in Discretionary Social Activities (SPDSA). These scores will be compared similar to the above aim. We hypothesize that IMPROVment® will have positive effects on daily function in people with PD.

C3 Rationale for the Selection of Outcome Measures

The following table details the outcome measures involved in this study. Members of the research team have been trained in the following measures.

Assessment	Description

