Participants will be recruited and screened for eligibility through the St. Louis Chapter American Parkinson's Disease Association (APDA). Approximately 15-20 participants diagnosed with PD will be recruited for this study. Consent will be obtained from each participant by select members of the research team. Each participant will be walked through the informed consent document in detail and allowed to ask questions with no cohesion. Participants will be re-assented to additional research processes after 9.24.2019 upon IRB reapproval.

2.d Randomization Method and Blinding

After consent is given and T1 testing is completed, participants will be randomly assigned (coin flip) to either participate immediately (i.e., starting the next week) in 12-weeks of IMPROVment (ID group) or to continue with regular routine for 12 weeks before starting IMPROVment (WC group). Once we reach 10 participants in a group, remaining participants will be assigned to the other group. In addition, if the participant would like to be a part of this study, but can only participate in one group or the other, we will try to accommodate his/her needs.

2.e Risks and Benefits

Risks:

Participation in this study could result in the following risks. In addition to these, there may be other unknown risks, or risks that we did not anticipate, associated with being in this study.

One risk of participating in this study is that confidential information about participants may be accidentally disclosed. We will use our best efforts to keep the information about participants secure.

Another risk of participating in this study is an increased risk for falls. Although we do not expect the participants to fall during the intervention, precautionary measures are in place to decrease this risk (i.e. certified therapist present at all times, OT students monitoring the participants, movement modifications sitting in a chair).

Benefits:

Participants will not directly benefit from being in this study. Participants may indirectly benefit from participating in this study with the increased social participation and entertaining nature of the study program.

However, we hope that, in the future, other people might benefit from this study because it will help to provide information on how people with PD can best learn and remember in their daily lives.

2.f When and How to Withdraw Subjects

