Participants may withdraw from this study at any time. To withdraw, participants will tell a member of the study team that he/she is no longer interested in participating in the study. He/she may withdraw completely from the dance classes or continue to dance and just withdraw from testing.

2.g Data Collection and Follow-up for Withdrawn Subjects

Data already collected on participants who withdraw from the study will be securely stored in a RedCap database. With the participants' consent, they may be used for comparison to those who remain in the study or for description of those who withdraw. If a participant would like to withdraw their data, they will be equipped with the procedure to follow on the Human Research Protocol Office website.

E3 Study Drug

NA

F Study Procedures

F1 Screening for Eligibility

Participants will be screened for eligibility using the “Inclusion/Exclusion Criteria Referral Form: IMPROVment® Class Participation” (Appendix 1)

F2 Schedule of Measurements

T1 testing will include the collection of demographics information, National Institute of Health Toolbox Cognitive Battery, the Weekly Calendar Planning Activity, Alternate Uses Task, and the Unified Parkinson's Disease Rating Scale Section 3 Motor exam.

Participants will also be asked to complete the Older Americans Resources and Services scale, Satisfaction with Participation in Discretionary Social Activities scale, the Parkinson Anxiety Scale, the Sleep Disturbance Scale, the Parkinson's Disease Fatigue Scale and the Depression Scale questionnaires. These questionnaires can be completed prior to the first day of intervention via RedCap survey mode or on paper if preferred. In addition, participants will be asked to complete a brief mood questionnaire at the beginning and end of each class. The participant will mark how they are feeling on 4 scales (see Appendix 4).

After the first 12 week period of intervention, both groups will be invited back to complete those same assessments (T2). After the second 12 week period, only the WC group will T3 testing with the same assessments.

F3 Class Structure

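### Optional improvement, not an error: add a baseline-adjusted analysis beside the planned change comparison, and a repeat without participants placed by preference or scheduling

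*Combined protocol and SAP*

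**What the plan says.** The analysis is described in the same terms throughout the combined protocol and SAP. The abstract ahead of A2 says "assessment scores will be compared across time point (T1, T2) and group (ID, WC) using mixed model ANOVA". C1 says "Cognitive test scores will be compared across time points (T1, T2) and between groups (ID, WC) using a mixed model repeated measures ANOVA". G3 says "Scores obtained in these assessments will be compared across time point and group using mixed model ANOVA" for Aim 1 and repeats this for Aim 2. G4 adds only the software. No baseline covariate is planned, and no term of the model is named as the treatment effect. G5 leaves people with missing data out of the analyses concerned.

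Allocation is by coin flip after T1, with two departures. The first is a cap in 2.d: "Once we reach 10 participants in a group, remaining participants will be assigned to the other group". The second is accommodation. E1 applies it "if someone has a strong preference or inability to participate in one group or the other due to scheduling issues", and 2.d applies it to someone who "can only participate in one group or the other, we will try to accommodate his/her needs". Neither G3 nor G5 treats these participants separately.

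On timing, E1 places the primary outcome measures of each aim in T1, and 2.d allocates once T1 testing is finished. F2 says of the self-report forms, which include OARS-Ex and SPDSA: "These questionnaires can be completed prior to the first day of intervention". G6 states that the study is not blinded.

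**The concern.** With 7 to 10 people per group (E1, G1), any interval will be wide. The T1 score is collected anyway, and adjusting for it can narrow the interval at no testing cost.

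People placed by preference or scheduling were not randomised. If they differ from the others, the change score and ANCOVA respond differently to that difference. A single unadjusted analysis of everyone gives the reader no means of seeing whether the result depends on them.

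The questionnaire window matters for Aim 2. By 2.d, the ID group starts the week after allocation. Under F2 a participant could therefore give T1 self-reports already knowing the group.

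**Working it through.** The plan gives no power, SD, effect size or T1-T2 correlation, so there is no figure of its own to reproduce.

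**Inputs.** From the documents: 7 to 10 per group (N = 14 to 20), two groups, two time points, complete cases. Assumed: normal scores, equal SDs at T1 and T2 (set to 1), and correlation rho of 0.5 to 0.9.

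**1. The planned term.** In a 2×2 mixed ANOVA on complete cases, the group-by-time F is the square of the t statistic comparing T2 minus T1 between groups.

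**2. Precision under coin-flip allocation.**
- Var(change) = 2(1 − rho)(1/n₁ + 1/n₂)
- Expected Var(ANCOVA) = (1 − rho²)(1/n₁ + 1/n₂)(N − 3)/(N − 4)
- Ratio = [(1 + rho)/2] × (N − 3)/(N − 4)

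The last factor is 17/16 = 1.0625 at N = 20 and 11/10 = 1.10 at N = 14.

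| rho | (1 + rho)/2 | 10 per group | 7 per group |
|---|---|---|---|
| 0.5 | 0.75 | 0.797 | 0.825 |
| 0.7 | 0.85 | 0.903 | 0.935 |
| 0.8 | 0.90 | 0.956 | 0.990 |
| 0.9 | 0.95 | 1.009 | 1.045 |

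The ratio reaches 1 at rho = 2(N − 4)/(N − 3) − 1, which is 0.88 (N = 20) or 0.82 (N = 14). On mean 95% CI width, counting the lost degree of freedom, break-even is about 0.87 and 0.80.

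**3. A stable gap between whole groups, no treatment effect.** Change has no bias. ANCOVA has bias (1 − rho) × gap. For a 0.5 SD gap this is 0.5 × 0.5 = 0.25, 0.3 × 0.5 = 0.15 and 0.2 × 0.5 = 0.10 SD at rho 0.5/0.7/0.8. In simulation with 10 per group, ANCOVA's type I error was 8.8/7.0/6.1%, and its mean squared error was 0.233 vs 0.200, 0.138 vs 0.119 and 0.092 vs 0.079 for change.

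**4. A few people placed by preference.** This is closer to what E1 and 2.d describe. Take 2 to 6 of 20, half in each group, with a stable 0.5 SD gap among them. The group means then differ by 0.5 × 2/20 = 0.05 to 0.5 × 6/20 = 0.15 SD. Multiplied by (1 − rho), ANCOVA's bias is 0.025 to 0.075 at rho 0.5 and 0.015 to 0.045 at rho 0.7. Simulation gave 0.02 to 0.07 over both. Mean squared error favours ANCOVA: about 0.16 vs 0.20 at rho 0.5, and 0.11 vs 0.12 at rho 0.7. The two roughly tie with 8 of 20 and a 1 SD gap (0.201 vs 0.199 at rho 0.5).

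**5. Placement that follows the T1 score itself.** With 10 per group ANCOVA is clearly better: 0.171 vs 0.261 at rho 0.5, and 0.117 vs 0.144 at rho 0.7.

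**6. T1 self-report given after allocation is known.** If this shifts T1 in one group by d, change is biased by −d and ANCOVA by −rho × d. For d = 0.3 SD: change −0.30; ANCOVA −0.15 (rho 0.5) or −0.21 (rho 0.7). Change is the more affected.

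**7. The restricted repeat.** Dropping 2/4/6 of 20 gives mean ANCOVA CI widths of 1.77/1.91/2.09 at rho 0.5, against 1.85 for full-sample change. At rho 0.7 they are 1.46/1.57/1.72 against 1.43.

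**The case against.** The strongest reply is that nothing here is broken. In a wait-list trial set up to test the effects of the class, a T1/T2 by ID/WC mixed ANOVA is ordinarily read as group by time. The study is a pilot with no power claim, and every precision figure rests on an assumed correlation. This stands, and it is why the point is optional. The additions also multiply estimates per measure, and the restricted repeat is often less precise than the planned analysis.

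Several stronger readings are tempting but unsupported:

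- A reader might infer that G3 has no usable treatment contrast. Not naming it is missing detail only.
- A reader might infer that ANCOVA should replace the planned estimate. Step 3 shows a case where ANCOVA is biased and change is not; steps 4 and 5 favour ANCOVA. The documents do not say how many people were placed by preference or why, so they do not settle which case applies.
- A reader might want a rule that calls the result uncertain when the two estimates differ materially. Under pure coin-flip allocation at rho 0.5 they differ by more than 0.25 SD in 26% (10 per group) to 32% (7 per group) of trials by chance alone. With the stable 0.5 SD gap the figure is only about 46%, so the rule would not discriminate.
- A reader might infer that the cap itself places many people. The expected number is 3.5 if 20 enrol, but 1.7 at 18 and 0.3 at 15, and the target is 15 to 20.
- A reader might infer from F2 that the Aim 2 baselines will be given after allocation. E1 and 2.d point the other way. F2 leaves room for it and no more.

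**Conclusion.** A cheap improvement, not an error. The planned comparison is valid under coin-flip allocation. Adjusting for T1 would cut variance by about 17 to 20% at rho 0.5 and 6 to 10% at rho 0.7, with little or no gain at 0.8 and a small loss at 0.9. Preference placement is a reason to show both estimates and a repeat without those participants; it does not justify switching the primary estimate.

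These sizes rest on assumed correlations, normal scores and equal SDs. OARS-Ex items run from 1 (best) to 5, so scores bunched at the best end could change its figures. Neither estimate cures unmeasured confounding or the rule in the exclusion criteria that "participants must attend at least ten of the twelve classes for their data to be included in analysis", which selects the ID group after allocation.

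**What to change.** Amend G3 for both aims:

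1. State that the treatment effect is group by time, reported as the ID minus WC difference in T2 minus T1 change with 95% CI, and that this estimate governs the conclusion. Report beside it a prespecified supportive ANCOVA of T2 on group, with the T1 score of the same measure as covariate. Show both, with no rule triggered by their difference.
2. Record each participant's route to a group (coin flip, cap, or preference/scheduling). As a sensitivity analysis, repeat both estimates without those placed by preference or scheduling.
3. Reconcile F2 with E1 and 2.d so that T1 OARS-Ex and SPDSA are completed before allocation. If any are completed later, flag both the change and the ANCOVA estimates.
4. Report T1 and T2 SDs and their correlation for each measure. G1 offers these data for sizing later trials, and those are the quantities needed.

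The cost is a few sentences, one allocation field and a questionnaire completion date. SPSS already fits ANCOVA. The downsides are one degree of freedom, no gain at high correlation, a less precise restricted repeat, and up to 2 × 2 = 4 estimates per measure, which is why one must be named as governing.
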